3.4 Evaluability for determining the MTD

Determination of the MTD in the dose escalation phase of the trial will be based on those patients who have received at least one cycle KTD and will be evaluated between the time of receiving the first dose of Carfilzomib in cycle 1 and the first dose of treatment in cycle 2. The safety review committee will review each DLT and attribute the DLT to the loading dose or the registered dose; any DLT attributed to the loading dose will be excluded when determining the MTD. KTD Patients who do not receive one complete cycle due to experiencing a DLT will be included in the analysis; patients who do not receive at least one complete cycle for reasons other than toxicity, without experiencing a DLT, and who miss a dose of Carfilzomib, more than 14 doses Thalidomide or 2 doses of Dexamethasone in the first cycle, will be replaced. Evaluability will be considered by the safety review committee on an individual basis to account for attributing DLTs and missed doses to the loading or the registered dose.

3.5 Dose Cohorts

The RD cohort will include all patients who are registered to receive and receive at least one dose of Carfilzomib at the RD. This cohort will include patients from the dose escalation and dose expansion phases

of the study. All patients who do not fulfil these criteria will be included in the non-RD cohort.

4. Data Handling

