
Treatment Summary:
	
KTD (maximum of 6 x 28 day cycles) KTD protocol
 
Days 1, 8,15 30 minute IV infusions of Carfilzomib at current dose level.
 
All patients will receive Carfilzomib at 20mg/m² on day 1 of cycle 1 and then registered dose level on day 8 of cycle 1 onwards. The dose levels are:
 
 • level -1- 27mg/m² • level 0 – 36mg/m² • level 1 – 45mg/m²

	
 level 2 - 56mg/m^{2s} 
Days 1-28 50mg Thalidomide, oral preparation for cycle 1 Up to 100mg can be considered for cycle 2 onwards
 
Days 1, 8,15 20mg Dexamethasone, oral preparation
 
A maximum of 6 cycles will be administered.

Anticipated duration of recruitment:	24 months
Duration of patient follow up:	Minimum 6 months after registration or 1 month after last cycle for each patient.
Definition of end of trial:	The end of trial is defined as the date of the last participant's last data item. At this point, the end of trial notification will be submitted to the relevant regulatory authorities (e.g. UK MHRA) and ethics committees.

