3.1 Aims

The Catalyst (*Carfilzomib-Dex in AL Amyloidosis treatment*) Trial aims to assess the safety and tolerability of KTD (Carfilzomib-Thalidomide-Dexamethasone) using the phase 1 dose escalating component to define the maximum tolerated dose (MTD) and recommended dose (RD) and the expansion cohort to further assess the safety and tolerability and to gain an understating of efficacy to allow design for further trials.

Primary:

Dose escalation

To define the MTD and RD of Carfilzomib used in combination with Thalidomide and Dexamethasone in patients with relapsed or refractory AL amyloidosis

Dose expansion

To further assess the safety and tolerability of KTD at the RD of Carfilzomib identified in the dose escalation phase

Secondary:

To make a preliminary assessment of the activity of KTD in patients with relapsed refractory AL amyloidosis

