8.1 Treatment Schedule Summary

8.1.1 KTD Regimen

All treatment will take place at the patient's RHC/Site.

If there is a ≥ 21 day delay in starting trial treatment after completion of eligibility confirmation form at the RHC, a second eligibility confirmation form must be completed. Patients must start treatment within 6 weeks of completion of the initial eligibility confirmation form.

Treatment will be as below with three regimes based on gradually increased dose and addition of Dexamethasone based on clonal response at end of each cycle.

KTD protocol – dose escalation phase

Carfilzomib

Days 1, 8,15

30 minute IV infusions of Carfilzomib at a dose according to table 1 below. A maximum of 6 cycles will be administered. All patients will be recommended oral hydration with 250 ml of fluids 2 hours before and one hour after the infusion at day 1. Oral hydration with 250 ml of fluids 2 hours before the infusion is recommended from day 8 onwards. Post infusion hydration is optional and at the discretion of the treating physician for patients at risk of tumour lysis syndrome and/or dehydration. Patients should be monitored closely for fluid overload.

All patients will receive Carfilzomib at 20mg/m² on day 1 of cycle 1 and then at the allocated dose level on day 8 and day 15 of cycle one, and during all subsequent cycles.

Thalidomide

1-28

50mg Thalidomide, oral preparation (potentially increasing to 100mg if well Days 1-28 tolerated - to be discussed with the Chief Investigator before increasing dose)

Dexamethasone

Days 1, 8,15

20mg Dexamethasone, oral preparation. This should be taken prior to all Carfilzomib doses.

Table 1: Dose Levels

Dose level	Carfilzomib IV (mg/m ²) (Days 1, 8 & 15)	Thalidomide (mg) (Days 1-28)	Dexamethasone (mg) (Days 1, 8 & 15)
-1	27	50	20
0	36	50	20
1	45	50	20
2	56	50	20

A minimum of 15 days must have elapsed between the start of treatment of the first patient in each cohort and subsequent patients.

KTD protocol – dose expansion phase

The dose escalation phase will then be extended once maximum tolerated dose (MTD) and the Recommended Dose (RD) has been established. All patients will then receive Carfilzomib-Thalidomide -Dexamethasone as follows (repeated every 28 days)

Carfilzomib Carfilzomib intravenous infusion at Recommended Dose (RD) .
Days 1, 8,15 A maximum of 6 cycles will be administered.

All patients will receive Carfilzomib at 20mg/m² on day 1 of cycle 1 and then RD from day 8 onwards

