19.2 General Considerations

Statistical analysis of clinical endpoint data is the responsibility of the CTRU Statistician. A full statistical analysis plan will be written before any analyses are undertaken. The analysis plan will be written in accordance with current CTRU standard operating procedures and will be finalised and agreed by the following people: the trial statistician and supervising statistician, the Chief Investigator, the CTRU Delivery and Scientific Leads and the Senior Trial Manager. Any changes to the finalised analysis plan, and reasons for changes, will be documented.

All patients that receive at least one dose of Carfilzomib and with no protocol deviations with relevant impact on safety will be included in the safety analysis set.

The per protocol set will include all patients with at least one post baseline efficacy assessment who receive at least one dose of Carfilzomib and have no protocol deviations with relevant impact on efficacy.

Determination of the MTD in the dose escalation phase of the trial will be based on those patients who have received at least one cycle KTD and will be evaluated between the time of receiving the first dose of Carfilzomib in cycle 1 and the first dose of treatment in cycle 2. The safety review committee will review each DLT and attribute the DLT to the loading dose or the registered dose; any DLT attributed to the loading dose will be excluded when determining the MTD.

KTD Patients who do not receive one complete cycle due to experiencing a DLT will be included in the analysis; patients who do not receive at least one complete cycle for reasons other than toxicity, without experiencing a DLT, and who miss a dose of Carfilzomib, more than 14 doses Thalidomide or 2 doses of Dexamethasone in the first cycle, will be replaced. Evaluability will be considered by the safety review committee on an individual basis to account for attributing DLTs and missed doses to the loading or the registered dose.

The RD cohort will include all patients who are registered to receive and receive at least one dose of Carfilzomib at the RD. This cohort will include patients from the dose escalation and dose expansion phases of the study. All patients who do not fulfil these criteria will be included in the non-RD cohort.

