2.1 Primary endpoint

Dose-Limiting Toxicities (Dose escalation phase), between the time of receiving the first registered dose of Carfilzomib in cycle 1 and day 1 cycle 2, in order to establish the Maximum Tolerated Dose (MTD) and recommended dose (RD) of Carfilzomib in combination with Thalidomide and Dexamethasone.

Proportion of patients treated who experience any grade 3 or 4 CTCAE toxicity throughout all treatment cycles.

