3.2 Safety analysis set

All patients that receive at least one dose of Carfilzomib and with no protocol deviations with relevant impact on safety will be included in the safety analysis set.

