5.3.2 Primary endpoints

The number of patients experiencing DLTs within the first cycle of KTD will be presented, with descriptive summaries of the specific DLTs observed. Summaries will be presented for each dose level. This data will be presented for patients registered to the dose escalation phase of the study only.

Further summaries of longer-term tolerability will also be presented for patients registered to the dose escalation phase to include the maximum toxicity grade experienced within the first three cycles of treatment, overall and by cycle. Individual listings of the toxicities, grade and cycle of all toxicities experienced within the first three cycles will be presented.

The number of patients experiencing any grade 3 or 4 CTCAE toxicity within all cycles of treatment will be summarised. This will be presented overall and by dose cohort, across all cycles as well as by each cycle.

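### Under SAP 3.5 a patient registered at the recommended dose (RD) who receives only the 20 mg/m² loading dose leaves the RD cohort, and SAP 5.1 gives an expansion patient of this kind no group at all

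*SAP*

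**What the plan says.** SAP 3.5 sets two conditions for the RD cohort, registration to the RD and receipt of a dose at the RD: "The RD cohort will include all patients who are registered to receive and receive at least one dose of Carfilzomib at the RD". Protocol 1.1 and 19.2 carry the same rule. The remainder are assigned explicitly: "All patients who do not fulfil these criteria will be included in the non-RD cohort".

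Protocol 8.1.1 fixes the start of treatment in the expansion phase: "All patients will receive Carfilzomib at 20mg/m² on day 1 of cycle 1 and then RD from day 8 onwards". The escalation phase uses the same 20 mg/m² start. The lowest dose level is "level -1- 27mg/m²"; the others are 36, 45 and 56 mg/m².

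The expansion aim in Protocol 3.1 is "To further assess the safety and tolerability of KTD at the RD of Carfilzomib identified in the dose escalation phase". The second primary endpoint in SAP 2.1 is "Proportion of patients treated who experience any grade 3 or 4 CTCAE toxicity throughout all treatment cycles", and SAP 5.3.2 says of it: "This will be presented overall and by dose cohort, across all cycles as well as by each cycle".

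The safety set in SAP 3.2 does not depend on dose size: "All patients that receive at least one dose of Carfilzomib and with no protocol deviations with relevant impact on safety will be included".

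SAP 5.1 describes the two groups differently from SAP 3.5. Its RD population is those treated at the recommended dose in either phase. Its non-RD population is limited to patients treated in the escalation phase at other dose levels, and is to be split by dose level.

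**The concern.** The loading dose is part of the regimen that the expansion phase is meant to assess, but a patient joins the RD cohort only on reaching a later, higher dose. Entry to the RD row of a primary toxicity endpoint thus depends on what happens in the first week, which belongs to the outcome being measured. If a patient stops early because of severe toxicity, that toxicity is taken out of the row describing the dose proposed for further trials and credited to patients treated at other doses.

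The SAP also disagrees with itself about where this patient goes: SAP 3.5 says the non-RD cohort, and SAP 5.1 has no place for an expansion patient. Two programmers could follow the SAP faithfully and produce different tables.

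**Working it through.** **Can the day 1 dose be at the RD?** The candidate levels are 27, 36, 45 and 56 mg/m² and the cycle 1 day 1 dose is 20 mg/m². None matches, so the earliest qualifying dose is cycle 1 day 8.

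**Where does a loading-dose-only patient registered at the RD go?**
- Safety set (SAP 3.2): included, absent a safety-relevant deviation.
- Overall grade 3/4 rate (SAP 5.3.2): included.
- RD cohort (SAP 3.5): excluded.
- Non-RD cohort (SAP 3.5): included.
- Non-RD population (SAP 5.1): an expansion patient does not qualify, so belongs to neither group.

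**Inputs for size.** The stated sample sizes reproduce: escalation minimum 3 + 3 = 6 and maximum 3 × 6 = 18, plus 20 in expansion (SAP 1.4). Protocol 8.1.3 requires at least 6 patients to have completed cycle 1 at the RD before expansion opens. I therefore assume n = 6 + 20 = 26 registered at the RD. Those 6 have passed day 8, so loading-dose-only patients among the 26 come from the 20 in expansion. The documents give neither an expected grade 3/4 rate nor a rate of stopping after the loading dose, so x and k below are assumptions.

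**Stops due to grade 3/4 toxicity.** Let x be the RD-registered patients with grade 3/4 toxicity and k those of them who stop before day 8. The RD rate is x/n if they are kept and (x − k)/(n − k) as written. The fall is k(n − x)/[n(n − k)], which is positive unless x = n.

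| x | kept in | k = 1 | k = 2 |
|---|---|---|---|
| 8 | 8/26 = 30.8% | 7/25 = 28.0% (−2.8 points) | 6/24 = 25.0% (−5.8) |
| 13 | 13/26 = 50.0% | 12/25 = 48.0% (−2.0) | 11/24 = 45.8% (−4.2) |

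The Clopper-Pearson 95% interval is 14.3% to 51.8% for 8/26 and 29.9% to 70.1% for 13/26, so 37.5 and 40.2 points wide. The SAP plans no interval for this endpoint; these are shown only for scale.

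**Stops without grade 3/4 toxicity.** Only the denominator shrinks. One such patient turns 8/26 = 30.8% into 8/25 = 32.0%, a rise of 1.2 points. With both kinds of stop, the RD rate falls only if the share with grade 3/4 toxicity among early stoppers exceeds x/n.

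**How likely is it to arise?** If each of the 20 expansion patients had a 2%, 5% or 10% chance of stopping after the loading dose for any reason (assumed), the chance of at least one is 1 − 0.98²⁰ = 33%, 1 − 0.95²⁰ = 64% or 1 − 0.90²⁰ = 88%.

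**The case against.** The strongest reply is that the phrase about the RD may mean a dose level rather than a milligram amount. Protocol 8.1.3 defines the RD as a dose level and speaks of completing cycle 1 at it, although that cycle always contains the 20 mg/m² dose. SAP 5.1, by leaving no non-RD place for expansion patients, fits that intention. This shows the wording is open to another reading, but it does not remove the problem. SAP 3.5 requires receipt of a dose at the RD in addition to registration, Protocol 8.1.1 separates the 20 mg/m² dose from the RD that follows it, and SAP 5.1 itself speaks of patients treated at the recommended dose. If the looser reading is intended, the text should say so.

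The reply also rightly limits the point. A reader might infer four stronger things that the documents do not support.

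- *That loading-dose toxicity vanishes from the primary results.* It does not. The overall rate keeps the patient. SAP 3.4 excludes loading-dose DLTs only from the MTD decision, and nothing removes them from the DLT summaries and toxicity listings for escalation patients in SAP 5.3.2. Toxicity on day 1 in a patient who goes on to a dose at the RD is counted in the RD row.
- *That the RD rate is always biased low.* That holds when the stop is due to grade 3/4 toxicity; other stops move it slightly up.
- *That the documents supply a stopping rate.* Protocol 2.1.3.1 reports grade 3 renal failure at cycle 1 day 2 in one of eight patients at 20 mg/m² (12.5%), but that patient stayed on study for the rest of cycle 1, under a twice-weekly schedule. The same section describes the first-dose reaction at 27 mg/m² and says prophylaxis has essentially eliminated it. Protocol 10.1, headed for the escalation phase only, provides for delay and discussion after severe loading-dose toxicity, so a stop is possible but not prescribed.
- *That the RD response rate is inflated.* Efficacy uses the per protocol set, which needs a post-baseline efficacy assessment (SAP 3.3). A patient without one is already excluded, whatever the cohort rule.

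**Conclusion.** The point holds in a limited form. Read as written, the plan moves a patient registered at the RD who stops after the loading dose out of the RD cohort, and SAP 3.5 and 5.1 disagree on where an expansion patient of this kind belongs. Only the RD and non-RD rows are affected.

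Where the stop is due to grade 3/4 toxicity, the RD rate is understated by about 2 to 3 points for one patient and 4 to 6 points for two. This assumes 26 patients at the RD and 8 or 13 of them with grade 3/4 toxicity. The shift is small beside the sampling uncertainty in a purely descriptive study, and how often it would arise is unknown. The reasons to act are that entry to the row depends on part of the outcome, that the row describes the dose carried forward, and that the two SAP sections need reconciling whatever the numerical effect.

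**What to change.** In SAP 3.5 and 5.1, and in Protocol 1.1 and 19.2:

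- define the RD cohort as all patients registered at the RD dose level who receive at least one dose of carfilzomib, including the 20 mg/m² loading dose;
- define the non-RD cohort as patients registered at other dose levels;
- list the patients who received only the loading dose, with their toxicities and reasons for stopping.

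The present definition can be kept as a sensitivity summary if the team wants toxicity among patients exposed to the RD itself.

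The cost is one aligned definition in four places. Registered dose level is already a key data item in SAP 4.2, so no new data are needed, and neither treatment nor the MTD rules change. The downside is that the RD cohort may include a few patients never exposed to the RD itself; the listing makes them visible.

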4.1 Data monitoring

Data will be monitored for quality and completeness by the CTRU. Missing data will be chased until it is received, confirmed as not available or the trial is at analysis. The CTRU will reserve the right to intermittently conduct source data verification exercises on a sample of participants, which will be carried out by staff from the CTRU. Source data verification will involve direct access to participant notes at the participating hospital sites and the collection of copies of consent forms and other relevant investigation reports. A Trial Monitoring Plan will be developed and a Meeting Group Monitoring Schedule including primary endpoint and safety data will be defined and agreed by the Trial Management Group (TMG) if necessary.

The Safety Review Committee will be acting as the data monitoring ethics committee and will review safety and ethics of the trial as described in the protocol.

The following will also be examined continuously during the course of the trial:

- Accrual
- Data quality
- Consent
- DLTs/SAEs/SUSARs
- Withdrawal from the trial
- Pregnancy
- Protocol deviations

4.2 Data validation

The Data Manager will carry out initial validation of the forms in accordance with the guidelines developed for the study. This will ensure that data is complete, consistent and up-to-date. Reasons should be obtained when data is unobtainable.

The database will also validate most dates and data in line with the pre-programmed validation rules in real time, as data is entered. Periodic batch validation will also be carried out to detect any data queries that may be missed if CRFs are entered in an order that does not allow the real time validation checks to work.

Key data items required are those for the primary endpoints and for withdrawal information. All key data items will be checked manually by the data managers (or their delegate) at the time of final analysis. Key data items include:

- Date of randomisation/registration
- Registered dose level
- Cycle number
- Drug compliance in first cycle to confirm evaluability for determining the MTD and analysis sets
- SAE/AE data

Additionally, data regarding withdrawal of consent is also classed as key data:

- Withdrawal of consent and date

In addition the statistician will validate the data to be used in the analysis in the following steps:

- The data will be read into permanent SAS data sets using the SAS data views procedure; the names and contents of the datasets can be found on the final database specification reports in the database documentation folder.

SAS will also be used to further validate the data and identify any missing or inconsistent data. Checks to be performed include:

- Eligibility checks (if not data management validations)
- Sequential dates (if not data management validations)
- Checks for unusual and outlying data (if not database validations)
- Checks for missing data (are there items of data which are systematically missing/do specific variables

- have a large amount of missing data etc) (if not database validations)
- Checks for inconsistencies in safety data
- Other checks as deemed appropriate

Any inconsistent data will be noted and an e-mail sent to the data manager responsible for the study (or their delegate). A copy of this e-mail will be kept in the statistician's trial file. All queries will be resolved, if possible in time for final analysis and the outcome documented.

5. Data Analysis

5.1 General calculations

Unless otherwise stated, percentages will be calculated using the total number of patients in the appropriate population as the denominator (i.e. including all patients with missing data for that variable). All analyses will be carried out using SAS unless stated otherwise.

All percentages and means will be rounded to 1 decimal place and standard deviations to 2 decimal places. Values that are below the limit of detection and therefore non-quantifiable will be summarised using the limit of quantification value. For listings, if required, the non-quantifiable value would be reported as an inequality.

Summaries are divided into those participants treated at the recommended dose either during the dose escalation phase (prior to the identification of the recommended dose) or during the dose expansion phase (RD population), and all other participants treated during the dose escalation phase at dose levels other than the recommended dose (Non-RD population). The non-RD population will be split by dose level.

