9.4 Clinical Management after Treatment Discontinuation

Patients whose underlying plasma cell dyscrasia does not respond by the end of three cycles or who have a clonal progression on treatment will be treated and followed up off trial at the discretion of the treating clinician but will have a final follow-up visit 6 months after registration.

Patients that receive 6 cycles of chemotherapy will be followed up 1 month after end of trial treatment.

Also refer to section 14 (Withdrawal of Patients) for further details regarding treatment discontinuation, patient withdrawal from trial treatment and withdrawal of consent to data collection.

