2.3.2 Secondary endpoints

Clonal response rate (based on paraprotein and FLCs) is defined as the proportion of patients who achieve at least a PR within 3 months, at 3 months, within 6 months and at 6 months after trial registration.

Amyloidotic organ response rate is defined as the proportion of patients who achieve organ response within 3

months and within 6 months of trial registration.

Time to Amyloidotic organ response is defined as the time from the dose allocation to first achieving organ response.

The number of patients experiencing dose delays will be defined as the number of patients experiencing delays in treatment with any of the study treatments.

KTD compliance: Patients will be regarded as compliant to treatment where treatment is received as per protocol until withdrawal from treatment and have no more than 1 dose omission of Carfilzomib, 5 of Thalidomide or 1 of Dexamethasone during each cycle.

Relative Dose intensity will be calculated as the percentage ratio between the received and planned dose intensities, where dose intensity is the cumulative dose divided by the duration of treatment.

3. Analysis Sets

Statistical analysis will be descriptive for all endpoints, and will be summarised overall and by dose cohort. All safety analyses will be based upon the safety analysis set; safety data from patients not included in this analysis set will be listed separately. All efficacy analyses will be based upon the per protocol set. Patients who do meet the criteria to be included in each of analysis sets will have the reasons for emission listed. A sensitivity analysis on the efficacy endpoints may be considered if the total number of patients in each of the analysis sets differs by more than 3 patients.

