5.3.2 Secondary endpoints

Safety and toxicity profiles for each cycle and cohort: data will be summarised descriptively, including the proportion of patients experiencing at least one SAE, the number of SAEs experienced per participant, and the number of SAEs experienced according to seriousness criteria, causality, and body system. Toxicity will be summarised according to CTCAE grades and will be summarised as the maximum grade toxicity experienced within each cycle, and overall.

The proportion of patients achieving at least a PR (clonal response) within 3m, at 3m, within 6m and at 6m and the proportion of patients achieving an amyloidotic organ response within 3m and 6m will be presented in tabulated form. Corresponding 90% and 95% confidence intervals will also be presented. Responses at 3 and 6 months will be broken down by response achieved, and by organ (for organ response).

Time to amyloidotic organ response and time to maximum response will be calculated using the Kaplan Meier method. Median time to amyloidotic organ response and median time to maximum response will be presented, with corresponding 95% confidence intervals.

The proportion and number of patients alive at 6 months and patients progression free at 6 months will be presented with corresponding 90% and 95% confidence intervals. If appropriate, Kaplan Meier curves for progression free survival may be explored.

Each patient will be assessed for their maximum clonal response; the number and proportion of participants in each response category within 6 cycles of treatment will be presented with corresponding 95% confidence intervals. Patients who do not achieve a maximum response will be summarised as, "no maximum response".

Feasibility of delivering treatment according to protocol schedule will be summarised descriptively to include the number of patients requiring dose delays and/or reductions, the number of patients withdrawing from treatment, and reasons for dose delays / reductions and withdrawals. Time on treatment and reasons for stopping treatment will also be presented. The number of doses missed will be summarised overall and by cycle.

6. Reporting and Dissemination of the Results

Final analysis will be carried out after the last participant's last data item.

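### The SAP's default denominator dilutes by-cycle safety percentages once patients have stopped treatment, most of all after the cycle-3 response gate

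*SAP*

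**What the plan says.** **Denominator.** SAP 5.1 sets the default: unless otherwise stated, "percentages will be calculated using the total number of patients in the appropriate population as the denominator", and it adds "including all patients with missing data for that variable".

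**Population.** SAP section 3 states "All safety analyses will be based upon the safety analysis set". SAP 3.2 defines that set as "All patients that receive at least one dose of Carfilzomib and with no protocol deviations with relevant impact on safety". The only further split is RD against non-RD, with non-RD by dose level (SAP 3.5 and 5.1). No population of patients who started or were dosed in a given cycle is defined.

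**By-cycle summaries.**
- SAP 5.3.2 Primary endpoints plans the number of patients with grade 3 or 4 toxicity: "This will be presented overall and by dose cohort, across all cycles as well as by each cycle".
- SAP 5.3.2 Secondary endpoints plans "Safety and toxicity profiles for each cycle and cohort: data will be summarised descriptively, including the proportion of patients experiencing at least one SAE".
- The same section has toxicity "summarised as the maximum grade toxicity experienced within each cycle, and overall".

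None of these states its own denominator, so the default applies to any percentage shown.

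**Who leaves treatment.** Protocol 8.1.1 allows up to six cycles. Protocol 11.2 makes continuation past cycle 3 depend on response. Protocol 9.4 moves off trial treatment those whose disease "does not respond by the end of three cycles", and those with clonal progression on treatment. Protocol 10.2 and 14.1.1 add stops for toxicity and other reasons. Protocol 13.2.1 ends adverse event recording 30 days after the last trial treatment.

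**The concern.** A patient who stopped at the cycle-3 gate receives no drug in cycles 4 to 6 and can add almost nothing to the numerator there, yet stays in the denominator. The number treated shrinks while the divisor does not. By-cycle percentages can then fall when the risk per treated patient is constant, and can stay flat when it is rising.

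The expansion phase exists to describe safety and tolerability at the RD. Someone planning a later trial would naturally read the cycle columns to judge how well cycles 4 to 6 are tolerated, and could wrongly conclude that tolerability improves with time.

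**Working it through.** The plan gives no by-cycle percentage and no expected attrition, so there is no figure of its own to reproduce.

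**Inputs from the documents**
- RD cohort: at least 6 escalation patients at the RD (Protocol 8.1.3) plus 20 in expansion (SAP 1.4). 6 + 20 = 26, if all are in the safety set.
- Maximum of six cycles, with a response gate after cycle 3.

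**Assumptions, not in the documents**
- Fraction still treated: 50% to 85%. For orientation only, in the phase I AL carfilzomib study described in Protocol 2.1.3.4, 7 patients were still on study and 5 had discontinued, 7/12 = 58%.
- Grade 3/4 risk among patients treated in a cycle: 25%, for illustration.
- Events after a patient's last dose are not booked to a cycle the patient never started. The SAP has no rule on this. With 28-day cycles and thalidomide to day 28, the 30-day recording window spans roughly one further cycle of calendar time, so the cycle-4 column depends on that rule.

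**Formula.** With x patients having an event, n treated in the cycle and N in the population:

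reported % = x/N = (x/n) × (n/N)

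The relative understatement of x/n is 1 − n/N.
- n/N = 0.50: 1 − 0.50 = 50%; 25% × 0.50 = 12.5%.
- n/N = 0.85: 1 − 0.85 = 15%; 25% × 0.85 = 21.25%, about 21%.

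**Constant risk, N = 26, assumed numbers on treatment**

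| Cycle | Treated n | Risk among treated | Printed (25% × n/26) |
|---|---|---|---|
| 1 | 26 | 25% | 25.0% |
| 2 | 25 | 25% | 24.0% |
| 3 | 24 | 25% | 23.1% |
| 4 | 18 | 25% | 17.3% |
| 5 | 16 | 25% | 15.4% |
| 6 | 14 | 25% | 13.5% |

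The printed figure almost halves with no change in risk.

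**Rising risk hidden.** 6/24 = 25.0%, 6/18 = 33.3% and 6/14 = 42.9% all print as 6/26 = 23.1%.

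**Whole-number examples with exact (Clopper-Pearson) 95% intervals**

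| Treated / 26 | Events | Of treated | Of all 26 |
|---|---|---|---|
| 20 | 5 | 25.0% (8.7 to 49.1) | 19.2% (6.6 to 39.4) |
| 15 | 4 | 26.7% (7.8 to 55.1) | 15.4% (4.4 to 34.9) |
| 13 | 3 | 23.1% (5.0 to 53.8) | 11.5% (2.4 to 30.2) |

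**The case against.** **The primary by-cycle text promises counts.** SAP 5.3.2 Primary endpoints speaks of the number of patients, and the 5.1 rule governs percentages. The proportion endpoint in SAP 2.1 runs over all treatment cycles, where the full safety set is the right divisor. This stands: a reader might infer that the primary endpoint is biased, and it is not. What remains is the SAE proportion, which is promised for each cycle, and any percentage printed beside the grade 3/4 or maximum-grade counts.

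**Missed doses.** These might seem to share the fault, but the SAP plans only their number by cycle. The denominator rule does not reach them.

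**The SAP does not code stopped patients as event-free.** True: it keeps them in the denominator and could show them in a separate row. The percentage with events is the same either way.

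**The appropriate population could mean those who started the cycle.** The words do not exclude this, but SAP section 3 names no such population, and retaining patients with missing data points the other way.

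**Attrition is reported elsewhere.** Withdrawals, reasons for stopping and time on treatment are all planned. That helps a careful reader but does not correct the percentages.

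**Events over all patients is a legitimate quantity, and conditioning on treatment selects.** Both are true. Those dosed in cycle 5 are mainly responders who tolerated treatment, so their percentage can look favourable for that reason. This calls for a footnote and a printed n; it does not justify leaving the diluted figure to be read as on-treatment risk.

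**The intervals overlap heavily.** They do, at this sample size. The dilution is nevertheless systematic and always in one direction.

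**Conclusion.** The point holds for by-cycle safety percentages. Following SAP 5.1 as written, each equals the on-treatment risk multiplied by the fraction still treated. The effect can begin in cycle 2 and should be largest after the cycle-3 gate. The direction follows from the text, given that events after the last dose are not assigned to unstarted cycles. The size rests on assumed retention: a relative understatement of 50% at 50% retention and 15% at 85%. Understated here means relative to the risk among patients treated in that cycle.

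A reader might be tempted to fix the size from the AL response rates cited in the protocol, for example 41% for lenalidomide with dexamethasone or 78% for carfilzomib. The documents do not support that. Those rates come from other regimens and are not retention at this trial's gate. Protocol 9.4 also does not say whether a minimal response (the MR category in Appendix 4) counts as responding.

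No decision in the trial depends on these columns. MTD and RD rest on cycle 1 DLTs, the analysis is descriptive, and counts and the across-all-cycles proportion are sound. The harm is to interpretation of later-cycle tolerability, and it is cheap to prevent.

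**What to change.** In SAP 5.1 and 5.3.2:

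1. State that by-cycle safety percentages use safety-set patients who received at least one dose of any trial drug in that cycle.
2. Print that n for every cycle, overall and by dose cohort.
3. State to which cycle events after a patient's last dose are assigned.
4. Keep the full safety set as denominator for the across-all-cycles figure.
5. Footnote the by-cycle tables: patients in later cycles are a selected group, mainly responders and those who tolerated treatment, so columns do not compare like with like.

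The cost is a few SAP sentences and an edit to the table shells. No new data are needed: cycle number and adverse event data are already key items in SAP 4.2, and Protocol 11.2 collects the dose given in each cycle. The one downside, selection in the later-cycle denominators, is what the footnote and per-cycle n disclose.
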